6.1 Overall Trial Design

This is an exploratory clinical (phase 2a), single-centre, prospective, randomised, vehicle-controlled, double-blinded, intra-individual comparison, split-face model (left/right design) trial. Subjects with moderate to severe acne vulgaris will be treated with LEO 43204 gel 0.018% and vehicle gel (i.e. the Investigational Products (IPs)). The IPs are administered as a thin wet layer to each treatment area (TA) on the left (TA_{left}) and right (TA_{right}) cheeks of the face, each area corresponding to approximately 36 cm² (refer to section [10.2.1](#)). Assessments during the trial are outlined in section [8.1](#).

The subjects will be enrolled sequentially into 4 cohorts (n=40 total).

Progression from one cohort to the next will be decided after a review of LSRs, safety and tolerability by the Safety Review Committee after Week 2 (Visit 7).

Handling of LSRs, safety or tolerability deemed unacceptable is described in section [12](#).

Cohort 1 (n=3): Treatment escalation with once daily application of IPs for one, two and three days respectively for each of the first three subjects.

Subjects will enter treatment sequentially such that the second and third subjects only are exposed after a safety evaluation of the preceding subject is done. The first subject will be dosed for one day only, the second subject up to two days and the third subject up to three days.

The safety evaluation that allows the next subject to be dosed consists of the maximal LSR score from evaluations at days 1, 2, 3, 4, 8 and week 2 or until considerable reduction of LSR score and any treatment related AEs has been observed.

For subjects two and three, the second and third treatment day depends on the following criteria:

- The subject not reporting intolerable response to treatment.
- The investigator not evaluating LSRs or treatment-related AEs to be unacceptable.
- The LSR scores not exceeding predefined criteria (see Table 1, section 6.1).

Subjects not receiving the optional treatment on Day 2 and/or Day 3 due to severe LSRs or treatment related AEs will remain in the trial and attend the scheduled follow up visits.

Cohort 2 (n=6): Once daily treatment for three days with the second and third day optional dependent on predefined criteria (see ‘Treatment Phase’ below) Two subjects may initiate treatment per week. The subjects will follow the same scheduled visits as in cohort 1.

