Non-inflammatory lesions	477345	657616	100

12 Trial Committees

The Safety Review Committee will comprise the following members:

- The International Coordinating Investigator
- Sponsor's medical expert
- Sponsor's Head of Translational Medicine
- Sponsor's pharmacovigilance expert
- Sponsor's Statistician
- The ICTM

Primary functions of the Committee:

- Operate to written procedures defined by the Safety Review Committee Charter for the trial.
- Document decision in the meeting minutes.

- Convene to review safety and tolerability after the last subject in cohort 1, 2 and 3 has completed the Week 2 follow-up visit (Visit 7).
- Decide whether quality of data is sufficient and whether unacceptable LSRs, safety or tolerability events have occurred necessitating termination of the clinical trial.

Prior to dosing of the first subject, the Safety Review Committee Charter will be finalised detailing the evaluation procedure and processes for immediate communication between sites.

Unacceptable LSR scores, safety and tolerability events:

Unacceptable safety and tolerability events in an individual subject are defined as 1) clinically relevant signs or symptoms observed, which in the opinion of the investigator are deemed unacceptable or 2) one or more of the following LSRs:

- Grade 4 crusting
- Grade 4 erosion / ulceration
- Grade 4 vesiculation / pustulation extending significantly outside the treatment area

Or two or more of the following:

- Grade 4 erythema
- Grade 3 crusting
- Grade 4 swelling extending significantly outside the treatment area
- Grade 3 erosion / ulceration
- Grade 3 vesiculation / pustulation

Criteria for terminating the trial:

The trial will be terminated if the perception of the benefit/risk ratio (judged from clinical symptoms, signs and/or (S)AEs) becomes unfavorable for the continuation of the trial.

- Any decision regarding premature termination of the entire trial will be made after mutual agreement between the Investigator and the sponsor.
- The sponsor reserves the right to cancel the trial at any time
- Due to the design of the trial, there are no statistical criteria for trial termination.
- The cumulative frequencies of subjects with unacceptable LSRs, safety and tolerability events (as defined above) that will strongly support the decision for trial termination are:

- 2 out of 3 subjects with unacceptable LSRs, safety and tolerability events after Cohort 1

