- 3 out of 9 subjects with unacceptable LSRs, safety and tolerability events after Cohort 2 (cumulative)
- 5 out of 15 subjects with unacceptable LSRs, safety and tolerability events after Cohort 3 (cumulative)

13 Electronic Case Report Forms and Data Handling

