16.1.1 Criteria for Premature Termination of the Trial and/or Trial Site

LEO, the investigator, the IRB/IECs or competent authorities may decide to stop the trial, part of the trial or a trial site at any time, but agreement on procedures to be followed must be obtained.

If a trial is suspended or prematurely terminated, the investigator must inform the subjects promptly and ensure appropriate therapy and follow-up. As specified by applicable regulatory requirements, the investigator or LEO must promptly inform IRB/IECs and provide a detailed written explanation. Relevant competent authorities must be informed.

The trial must be terminated if the perception of the benefit/risk ratio (judged from clinical signs and symptoms, (S)AEs and/or remarkable safety laboratory changes) becomes unfavorable for the continuation of the trial.

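### In Cohorts 2 and 3 the cumulative counts that support termination can be reached before the cohort is fully dosed, but the protocol ties no interim tally or committee meeting to them

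*Protocol*

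**What the plan says.** Protocol section 6.1 places the decision between cohorts: "Progression from one cohort to the next will be decided after a review of LSRs, safety and tolerability by the Safety Review Committee". It times that review to Visit 7, the Week 2 visit. Section 12 repeats the timing; the committee is to "Convene to review safety and tolerability after the last subject in cohort 1, 2 and 3 has completed the Week 2 follow-up visit". Section 11.3.10 also puts the interim analysis after Week 2, uses blinded data, and counts a subject who meets the local skin response (LSR) definition at any time.

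Section 12 then lists the cumulative frequencies that would lend strong support to terminating: for Cohort 1, two of its three subjects; for the next look, "3 out of 9 subjects with unacceptable LSRs, safety and tolerability events after Cohort 2 (cumulative"); and 5 of 15 after Cohort 3, also cumulative. It adds that there are no statistical criteria for termination.

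On pace, section 6.1 doses Cohort 1 one subject at a time, each after a safety evaluation of the one before. For Cohort 2 (n=6), "Two subjects may initiate treatment per week". Cohort 3 (n=6) has no weekly limit.

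On who may stop, section 12 states: "Any decision regarding premature termination of the entire trial will be made after mutual agreement between the Investigator and the sponsor". Its next bullet reserves the sponsor's right to cancel at any time. Section 16.1.1 says that the sponsor, the investigator, the IRB/IECs or the authorities "may decide to stop the trial, part of the trial or a trial site at any time", with agreement needed on the procedures to be followed.

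**The concern.** Staggered starts in Cohort 2 are useful because the results of earlier subjects can be seen before later ones are exposed. Section 3.3.1 says that the measures in sections 6.1 and 12 are there for early detection of unexpected severe events, in a population for which section 3.4 says no data exist. Yet the counts are attached only to cohort-end meetings. If the third event falls among the first two or four subjects of Cohort 2, the 3-of-9 figure is settled, and neither section says that anyone must notice before the remaining subjects start.

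At stake is exposure of a few subjects after the plan's own warning figure has been reached, without the committee having considered it. If the investigator and the sponsor then disagree about stopping, the termination passages do not give a single answer.

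**Working it through.** **The plan's denominators.** Cohort sizes are 3, 6 and 6 (section 6.1). Cumulatively these are 3, 3+6=9 and 3+6+6=15, which agree with section 12. The documents state no event rate and no operating characteristics for the counts, so there are none to reproduce.

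**Range of subjects started after a count is reached.**
- Cohort 2 is entered without the 2-of-3 count being met, so with at most 1 event. The third event can come at the earliest at subject 5 of 9, leaving 9−5=4.
- Cohort 3 is entered without the 3-of-9 count being met, so with at most 2 events. The fifth event can come at the earliest at subject 12 of 15, leaving 15−12=3.
- The minimum is 0 in each: the last needed event may come at the end, or never. If all six Cohort 3 subjects start together, the number is also 0.

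**Cohort 2 probabilities.** Assumptions: independent events at rate p, three successive pairs, and each pair's events known before the next pair starts. Let
- P0=(1−p)³ and P1=3p(1−p)², the chances of 0 and 1 events in Cohort 1; entry E=P0+P1;
- R = P1·Pr(Bin(4,p)≥2) + P0·Pr(Bin(4,p)≥3), the count reached before the last pair starts;
- S = P1·Pr(Bin(6,p)≥2) + P0·Pr(Bin(6,p)≥3), the count reached by the end of Cohort 2;
- Q = P1·p², the count reached by the first pair, with 4 subjects still to start. If it is reached at the second pair, 2 are still to start.

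The mean number of extra subjects is [4Q+2(R−Q)] divided by S (given 3 of 9 is reached) or by E (given entry only).

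Example at p=50%: P0=0.125, P1=0.375. R=0.375×0.6875+0.125×0.3125=0.297. S=0.375×0.8906+0.125×0.6563=0.416. R/S=71% and R/E=0.297/0.5=59%. Q=0.375×0.25=0.094, so the mean given S is (4×0.094+2×0.203)/0.416=1.9.

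| Assumed rate p | R | S | E | R/S | Mean extra, given S | R/E | Mean extra, given E |
|---|---|---|---|---|---|---|---|
| 10% | 0.015 | 0.039 | 0.972 | 39% | 0.9 | 1.6% | 0.04 |
| 20% | 0.083 | 0.183 | 0.896 | 46% | 1.1 | 9% | 0.22 |
| 33% | 0.214 | 0.383 | 0.741 | 56% | 1.4 | 29% | 0.71 |
| 50% | 0.297 | 0.416 | 0.500 | 71% | 1.9 | 59% | 1.56 |

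If Cohort 2 subjects instead start one at a time with outcomes known at once, the conditional chance rises to 66%, 77% and 88% at rates of 10%, 30% and 50% (mean 1.3, 1.7 and 2.3). If outcomes emerge later than assumed, fewer of these exposures could have been foreseen.

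**Cohort 3.** With one-at-a-time starts (an upper bound), given that 5 of 15 is reached, the chance is 51%, 61% and 73% at 10%, 30% and 50% (mean 0.8, 1.0 and 1.3). The chance that Cohort 3 is the first look at which a count is met is small: 0.3%, 7.4% and 4.9%.

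**Who may terminate.** One section 12 bullet requires both parties to agree on any premature termination of the entire trial. The next lets the sponsor cancel at any time, and section 16.1.1 gives any of four parties the power to stop. Section 14 lets the investigator halt temporarily for an immediate hazard without prior approval. The sponsor's power therefore appears in both section 12 and section 16.1.1. What remains unsettled is mainly whether the investigator alone may end the trial.

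**The case against.** The strongest reply is that the counts were never meant as running boundaries. They are defined after each cohort and feed a benefit/risk judgement. That stands. A reader might infer that a binding trigger is being ignored, or that later subjects add nothing to the decision. The documents support neither: 3 of 9 and 6 of 9 are different findings, and severity and resolution up to Week 2 also bear on the judgement.

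A reader might also infer that nobody watches between meetings. That is wrong too. This is one site, staff apply every dose, subjects are seen daily from Day 1 to Day 4, Table 1 governs each repeat application, and sections 12, 14 and 16.1.1 allow stopping at any time. Cohort 1 is largely covered by its one-at-a-time dosing, although that step is not tied to the 2-of-3 count.

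The charter, due before first dosing, may already provide for a tally. It is not among the documents, so only the protocol's silence can be asserted.

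The timing assumption is also open to challenge. The Day 3 peak in section 10.3.1 comes from an actinic keratosis trial, the protocol says responses in acne may differ, and two starts per week need not be seven days apart.

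What survives is narrower: a discretionary power to stop helps only if someone knows that the figure has been reached, and the protocol assigns that task to no one within Cohorts 2 and 3.

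**Conclusion.** The point holds in limited form. Within a single look the count cannot fall, the scheduled review comes only after the cohort's last Week 2 visit, and no protocol passage links a running tally or an early meeting to the counts in Cohorts 2 and 3. Subjects can, not will, start treatment after a count is reached.

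The size depends strongly on the unknown event rate. At 10% the gap rarely matters for a trial entering Cohort 2; at 33% to 50% it matters often. Independence, pairwise starts and timely knowledge of events are assumptions. The certainty does not carry across looks: the figure rises from 3 at 9 subjects to 5 at 15, so a third event during Cohort 3 is not itself a flag.

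On termination, one might read sections 12 and 16.1.1 as wholly opposed. They are not, because section 12 itself lets the sponsor cancel. The mutual-agreement bullet still contradicts the at-any-time powers as written, and the passages must be reconciled.

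This is a worthwhile, inexpensive improvement rather than a flaw that undermines the trial.

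**What to change.** In section 12 and the charter, state that the existing blinded counts are tallied as events are recorded in Cohorts 2 and 3, and that the committee convenes when a stated count is reached as well as at the planned cohort-end reviews. If the charter already says this, a cross-reference in section 12 is enough. The counts themselves, and any clinical action including what happens to further starts, stay with the sponsor.

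Separately, reconcile the mutual-agreement bullet in section 12 with the bullet after it and with section 16.1.1, so that it is clear whether the investigator alone may terminate.

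The cost is wording and possibly one unscheduled meeting. Section 13.2 already asks for data entry as soon as possible after each visit, and no unblinding is needed because the section 11.3.10 reviews use blinded data.

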13.1 Electronic Case Report Forms (eCRFs)

Data will be collected by means of Electronic Data Capture (EDC). The investigator or staff authorised by the investigator must enter subject data into electronic CRFs. Data recorded in the electronic CRFs must be accessible to site staff through a secure internet connection immediately after entry. The eCRFs must be maintained in an up-to-date condition at all times.

The investigator must electronically sign all CRFs used. This signature information (including date of signature) will be kept in the audit trail and cannot be altered. Any correction(s) made by the investigator or authorised site staff to the eCRF after original entry will be documented in the audit trail. Changes to data, already approved, will require the re-signature of the investigator. The person making the change and the date, time and reason for the change will be identified in the audit trail.

For archiving purposes, each investigator must be supplied with a copy of the eCRFs for all subjects enrolled at the trial site via an electronic medium at completion of the trial and before access to the eCRF is revoked. Audit trail information must be included. eCRFs must be available for inspection by authorised representatives from LEO (e.g. audit by the quality assurance department), from regulatory authorities and/or IEC/IRBs.

13.2 Data Handling

Subject data should be entered into the eCRF as soon as possible after the visit in accordance with the time requirements described in the Clinical Trial Agreement with the site. Queries for discrepant data may be generated automatically by the system upon entry or generated manually by the monitor or the trial data manager. All queries, whether generated by the system or by a user, will be in an electronic format. This systematic validation will ensure that a clean and consistent database is provided prior to the statistical analysis being performed.

13.3 Source Data

For all data recorded, the source document must be defined in a source document agreement at each trial site. There must only be one source defined at any time for any data elements.

The trial monitor will check the eCRFs for accuracy and completeness by verifying data recorded in the eCRF against source data to ensure such records are consistent.

Source data should as a general rule be recorded in the subject's medical record or other defined document normally used at the trial site. Source data not normally collected as a routine part of the clinical practice at the site may be entered on a worksheet. Clinical assessments/safety evaluations must be signed by medically qualified (sub)investigators.

- If the worksheet does not become part of the subject's medical record, the following should as a minimum be added to the subject's medical record:
- Date(s) of conducting the informed consent process (date of enrolment) including date of provision of subject information
- Subject ID
- Randomisation code number (if applicable)
- The fact that the subject is participating in a clinical trial in acne including treatment arms of LEO 43204 gel and vehicle gel once daily for up to three consecutive days
- Other relevant medical information

13.4 Trial Monitoring

During the course of the trial, the monitor will visit the trial site to ensure that the protocol and GCP are adhered to, that all issues have been recorded to perform source data verification, and to monitor drug accountability.

The first monitoring visit should be performed as soon as possible after First Subject First Visit (FSFV) and no later than 4 weeks after.

The monitoring visit intervals will depend on the trial site's recruitment rate, the compliance of the trial site with the protocol and GCP.

In order to perform their role effectively, monitors and persons involved in quality assurance and inspections will need direct access to source data, e.g. medical records, laboratory reports, appointment books, etc. If the electronic medical record does not have a visible audit trail, the investigator must provide the monitor with signed and dated printouts. In addition, relevant

site staff should be available for discussions at monitoring visits and between monitoring visits (e.g. by telephone).

14 Handling of an Urgent Safety Measure

An Urgent Safety Measure is a measure taken to implement an action/protocol deviation under an emergency. This is defined within the EU Directive as “...*the occurrence of any new event relating to the conduct of the trial or the development of the investigational medicinal product where that new event is likely to affect the safety of the subjects, the sponsor and the investigator shall take appropriate urgent safety measures to protect the subjects against any immediate hazard.*” (Article 10(b) of Directive 2001/20/EC).

If the investigator becomes aware of information that necessitates an immediate change in the clinical trial procedure or a temporary halt to the clinical trial in order to protect clinical trial subjects from any immediate hazard to their health and safety, the investigator can do so without prior approval from LEO, regulatory authority(ies) or IRB(s)/IEC(s).

The investigator must immediately inform LEO - by contacting the ICTM or medical expert - of this change in the clinical trial procedure or of the temporary halt providing full details of the information and the decision making process leading to the implementation of the urgent safety measure.

LEO must act immediately upon receipt of the urgent safety measure notification in accordance with the internal procedures.

15 Quality Assurance/Audit

The clinical trial will be subject to audits conducted by LEO or inspections from domestic or foreign regulatory authorities or from IRBs/IECs. Audits and inspections may take place during or after the trial. The investigator and the site staff as well as LEO staff have an obligation to cooperate and assist in audits and inspections. This includes giving auditors and inspectors direct access to all source documents and other documents at the trial site relevant to the clinical trial. This includes permission to examine, verify and reproduce any records and reports that are important to the evaluation of the trial.

If the trial site is contacted for an inspection by competent authorities, LEO must be notified immediately.

16 Completion of Trial

16.1 Trial Completion Procedures

Trial enrolment will be stopped at the trial site when the total requested number of subjects for the clinical trial has been obtained.

Upon completion of the clinical trial, LEO must undertake arrangements for the collection and disposal of any unused trial material that the investigator is not required to keep in his/her files.

16.1.1 Criteria for Premature Termination of the Trial and/or Trial Site

LEO, the investigator, the IRB/IECs or competent authorities may decide to stop the trial, part of the trial or a trial site at any time, but agreement on procedures to be followed must be obtained.

If a trial is suspended or prematurely terminated, the investigator must inform the subjects promptly and ensure appropriate therapy and follow-up. As specified by applicable regulatory requirements, the investigator or LEO must promptly inform IRB/IECs and provide a detailed written explanation. Relevant competent authorities must be informed.

The trial must be terminated if the perception of the benefit/risk ratio (judged from clinical signs and symptoms, (S)AEs and/or remarkable safety laboratory changes) becomes unfavorable for the continuation of the trial.

16.2 Provision for Subject Care Following Trial Completion

After the completion of the trial, the subjects will be treated at the investigator's discretion or referred to other physician(s) according to standard practice.

16.3 Archiving of Trial Documents

The investigator at each trial site must make arrangements to store the essential trial documents including the Investigator Trial File (ICH E6, Guideline for Good Clinical Practice) until LEO informs the investigator that the documents are no longer to be retained or longer if required by local regulations.

In addition, the investigator is responsible for the archiving of all relevant source documents so that the trial data can be compared against source data after the completion of the trial (e.g. in case of an inspection from regulatory authorities).

The investigator is required to ensure the continued storage of the documents even if the investigator leaves the clinic/practice or retires before the end of the required storage period.

The destruction process must ensure confidentiality of data and must be done in accordance with local regulatory requirements.

17 Ethics and Regulatory Authorities

17.1 Institutional Review Boards (IRBs)/Independent Ethics Committees (IECs) and Regulatory Authorities

Written approval or favourable opinion must be obtained from relevant IRB/IECs prior to the enrolment of subjects.

Any amendments to the approved clinical trial must be approved by/receive favorable opinion from relevant IRBs/IECs and regulatory authorities as required prior to the implementation.

The appropriate regulatory authority(ies) must be notified of/approve the clinical trial, as required.

